	
Subjects will be evaluated in 2 strata:
 
 • Stratum 1: Subjects that are in remission at the end of upfront therapy defined as chemotherapy (5-7 cycles), surgery as indicated, consolidation therapy as indicated, radiation therapy as indicated, anti-GD2 antibody therapy with retinoic acid up to 6 cycles. • Stratum 2: Subjects that are in remission after any previous relapse or refractory therapy 
Stratum 1- A total of 127-140 subjects in Stratum 1 will be enrolled to ensure that there will be 127 evaluable subjects.
 
Stratum 2- A total of 38 subjects in Stratum 2 will be enrolled to ensure that there will be 33 evaluable subjects.

ELIGIBILITY
	
Inclusion Criteria
 
 1. Age: 0-21 years at the time of diagnosis. 2. Diagnosis: histological verification at either the time of original diagnosis or a previous relapse of high risk neuroblastoma. 3. Disease Status: Neuroblastoma that is in Remission 4. Greater than 30 days from completion of cytotoxic and antibody therapy and less than 120 days from previous therapy. 5. A negative serum or urine pregnancy test is required for female subjects of child bearing potential (onset of menses or ≥ 13 years of age). 6. Both male and female post-pubertal study subjects need to agree to use one of the more effective birth control methods during treatment and for six months after treatment is stopped. These methods include total abstinence (no sex), oral contraceptives (“the pill”), an intrauterine device (IUD), levonorgestrol implants (Norplant), or medroxyprogesterone acetate injections (Depo-provera shots). If one of these cannot be used, contraceptive foam with a condom is recommended. 7. ANC > 500/μl and platelet count >50,000/μl 8. Organ Function Requirements

Subjects must have adequate liver function as defined by
 AST and ALT <10x upper limit of normal
 Serum bilirubin must be ≤ 2.0 mg/dl
 Serum creatinine based on age/gender as follows:

Age	Maximum Serum Creatinine (mg/dL)	
	Male	Female
1 month to < 6 months	0.4	0.4
6 months to < 1 year	0.5	0.5
1 to < 2 years	0.6	0.6
2 to < 6 year	0.8	0.8
6 to < 10 years	1	1
10 to < 13 years	1.2	1.2
13 to < 16 years	1.5	1.4
≥ 16 years	1.7	1.4

9. Informed Consent: All subjects and/or legal guardians must sign informed written consent. Assent, when appropriate, will be obtained according to institutional guidelines

Exclusion Criteria

1. Lansky score < 60%

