2. BSA (m²) of <0.25
3. Investigational Drugs: Subjects who are currently receiving another investigational drug are excluded from participation.
4. Anti-cancer Agents: Subjects who are currently receiving other anticancer agents are not eligible. Subjects must have fully recovered from the effects of prior chemotherapy (hematological and bone marrow suppression effects).
5. Infection: Subjects who have an uncontrolled infection are not eligible until the infection is judged to be well controlled in the opinion of the investigator.
6. Subjects who, in the opinion of the investigator, may not be able to comply with the safety monitoring requirements of the study, or in whom compliance is likely to be suboptimal, should be excluded.

	
Additional criteria:
 
Subjects willing to participate in the correlative biologic studies will sign an additional consent form to provide bone marrow and blood for analysis.

ESTIMATED NUMBER OF SUBJECTS/GEOGRAPHIC REGIONS	A projected total of 160 evaluable subjects (Stratum 1-127 subjects, Stratum 2-33 subjects). Up to 25 sites in the United States will participate.
LENGTH OF STUDY	Accrual to this study is estimated to be at least 2 years, with follow up until all patients meet primary and secondary endpoints.
INVESTIGATIONAL PRODUCT DOSE/ROUTE/REGIMEN	
DFMO is an oral tablet that will be administered daily on a 28-day cycle.
 
Dose will be 500 to 1000mg/m² given BID (per dosing chart in section 6.1.2)

STUDY ASSESSMENTS	Refer to Table of Assessments for timing of study procedures.

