9.2 Criteria for Subject Off-Study

Subjects may be withdrawn from the study completely which includes survival follow-up for the following reasons:

- Subject or guardian withdraws consent to continue in the trial
- Subject is lost to follow-up (defined as the inability to contact the subject on 3 separate occasions over a period of 2 weeks)
- Subject completes all protocol defined therapy including all follow-up time points.
- Death

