10.2 Statistical Analysis

This is an open label, single agent, multicenter, study for patients with neuroblastoma that are in remission.

The following data sets will be used in this study:

- All enrolled and eligible subjects (ITT) population: All eligible subjects who have a signed informed consent form.
- All treated and eligible subjects (Safety evaluable) population: All subjects who received at least one dose of study drug
- All eligible subjects treated to first evaluable time point with evaluation completed (generally 3 cycles) (as Treatment Efficacy) population, unless subjects have reached the study endpoint of progression of disease at an earlier time point.

Efficacy analyses will be performed on the Treatment evaluable population. Safety analysis will be performed on the Safety and Efficacy evaluable population.

10.3 All baseline patient characteristics will be summarized in a tabular format. Safety data will be described for all subjects receiving at least one dose of DFMO. Safety data will include values for hematology, serum chemistry, vital signs, and adverse events. The proportion of subjects experiencing adverse events, serious adverse events, dose limiting toxicities and treatment delays will be summarized. Enrollment to study will not pause at interim analysis time points.

Sample Size and Analysis:

Stratum 1:

A 70% 2-year EFS rate was selected as the Phase I baseline rate. The baseline 70% EFS rate at 2-years was based upon published data by Yu et al. (82). It is hypothesized that DFMO will increase the 2-year EFS rate to 80% which represents an approximately 10% increase in the duration of the EFS rate at 2-years. Assuming a directional 5% one population binomial test, a sample size of $n = 127$ patients will be required to achieve an 80% power to detect this 2-year difference in EFS (70% vs 80%).

The comparison of the biomarker prevalence rates assumes that the Stratum 1 cohort will experience a relapse rate of 30% and thus a 70% non-relapse rate at up to two years of follow-up. It is also assumed that the corresponding prevalence of an elevated biomarker will be 60% for the relapse group and 30% in the non-relapse group, respectively. This hypothesized prevalence difference will be detectable with 85% power with an overall sample size of N=127 patients (38 relapse and 89 non-relapse) using a Fisher's Exact Test and a non-directional Type I Error level of 5%.

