Based upon tabled median EFS times all patients presented by Santana et al. (Cancer, June 15, 2008) for first and second recurrence times, a median first recurrence time of 8.7 months is equivalent to a 14.8% EFS at two years, and the median time to a subsequent second recurrence of 3.8 months is equivalent to an EFS rate of 1.3% at two years assuming an exponential time-to-event model. Assuming that two thirds of the relapse patient population will have had only a single relapse and that the other third of the patients will have had two or more relapses, then a weighted average of these two EFS rates (14.8% and 1.3%) equals 10.3%. A 10% historical EFS rate for two years was assumed for simplicity. Examination of an increase in EFS will require a sample size of n = 33 subjects in Stratum 2 to test whether treatment with DFMO can prolong the overall estimated EFS at two years to 30% from the 10% two years estimate for the above historical data in this patient population. The sample size is based upon a one sample binomial test of proportions with a power 80% and a 5% two -tailed Type I error level.

An observation of 7 or more patients with at least a two year EFS rate out of the $n = 33$ patients will result in the rejection of the null hypothesis of a 10% EFS in favor of the alternative of a 30% two year EFS rate. An exact binomial 95% confidence interval for the two year estimated EFS will complement the prior formal two-stage hypothesis test. Since the actual EFS time-to-event data is derived from the times to recurrence, a Kaplan-Meier analysis of the time-to-event data analysis will be conducted, and the median time to recurrence and a 95% confidence for this value will be obtained to supplement this EFS point estimate. Since this group of Stratum 2 patients will consist of patients with prior single and multiple recurrence histories, EFS and time to event data will be examined by prior recurrence histories. In particular, the impact of prior recurrence history on the time to recurrence will be explored using Kaplan-Meier analysis and Cox proportional hazard models. The response to DFMO therapy and subsequent recurrences will also be explored in combination with prior recurrence histories using Cox models.

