10.4 Event Free Survival

The event free survival (EFS) is defined as the period from the first day of administration of study drug until the first occurrence of relapse, progressive disease, secondary cancer, or death or, if none of these events occurred, until the last contact with the subject.

Progression is defined as the appearance of any new lesions >10mm on CT/MRI, any new lesions on MIBG or new disease present in the bone marrow.

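### Stratum 1: the only EFS test named needs every patient's 2-year status, and the plan gives neither a Kaplan-Meier estimate of EFS nor a rule for evaluable patients lost event-free before 2 years

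*Combined protocol and SAP*

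**What the plan says.** Section 10.4 measures EFS from the first dose to the first event or, "if none of these events occurred, until the last contact with the subject". The word censored is used only for OS (section 10.5), but the effect for EFS is the same.

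For Stratum 1, the Sample Size and Analysis text in section 10.3 (and the synopsis) says: "Assuming a directional 5% one population binomial test, a sample size of" 127 gives 80% power for 70% versus 80% at 2 years. It gives no rejection count, confidence interval or Kaplan-Meier estimate for the Stratum 1 EFS rate. Kaplan-Meier and Cox methods do appear under Stratum 1, but for the biomarker comparison.

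Efficacy is analysed in the set described in section 10.2 as "All eligible subjects treated to first evaluable time point with evaluation completed (generally 3 cycles"), or with earlier progression. The synopsis states: "A total of 127-140 subjects in Stratum 1 will be enrolled to ensure that there will be 127 evaluable subjects".

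Section 9.2 lists reasons for which a subject may leave the study completely, survival follow-up included. Two of them are "Subject or guardian withdraws consent to continue in the trial" and "Subject is lost to follow-up (defined as the inability to contact the subject on 3 separate occasions over a period of 2 weeks").

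The synopsis plans a study "with follow up until all patients meet primary and secondary endpoints". Section 7.10 collects remission status, as well as survival, after therapy ends.

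Stratum 2 is specified more fully. It has a rejection count (7 of 33), an exact confidence interval and, for EFS, "a Kaplan-Meier analysis of the time-to-event data analysis will be conducted".

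**The concern.** A one-sample binomial test classes each patient as event-free at 2 years or not. A patient who passes the first evaluation and is then lost event-free is in the efficacy set but belongs to neither class. The 127-140 enrolment range replaces non-evaluable patients. It does not cover patients lost after they become evaluable.

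Three ways of counting are open: failure, exclusion or event-free. If loss is independent of outcome, the first two bias the 2-year rate downwards and the third upwards. Kaplan-Meier uses the observed follow-up without that bias.

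The choice can decide the result. Suppose 94 patients are event-free at 2 years, 27 have events and 6 are lost. As failures, 94/127 does not reject. Dropped, 94/121 rejects (cut-off 94, exact p = 0.038). As event-free, 100/127 rejects. In an open-label single-arm trial, a rule fixed late could be fixed with the results in view.

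**Working it through.** **Inputs from the documents.** Null 70%, alternative 80%, one-sided 5%, n = 127, up to 140 enrolled (synopsis; section 10.3). First evaluation after 3 cycles: 3 × 28 = day 84. Two years is taken as day 730.

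**Inputs assumed.** The documents give no loss rate, so I use d = 2%, 5% and 10% per 2 years. Event times are exponential with 2-year EFS p. Loss is independent and exponential, and acts only from day 84.

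**Step 1: the plan's own figure.** The smallest k with P(X ≥ k | 127, 0.70) ≤ 0.05 is 98. Exact type I error is 0.0453 and power at 0.80 is 0.8196, so n = 127 for 80% power is reproduced. The expected count at 80% is 127 × 0.80 = 101.6, which is 3.6 patients above the cut-off. At n = 140 the cut-off is 108, type I error 0.0374 and power 0.8298.

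**Step 2: loss model.** With λ = −ln(p)/730 and μ = −ln(1−d)/730 per day:
- observed event-free at 2 years: s = p(1−d)^(646/730), where 646 = 730 − 84
- lost event-free before 2 years: L = exp(−84λ) × μ/(λ+μ) × [1 − exp(−646(λ+μ))]

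At p = 0.80, 127 × L = 1.99, 4.99 and 10.01 patients for d = 2%, 5% and 10%.

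**Step 3: counting rules.** Failures use success probability s. Event-free uses s + L. Dropped uses s/(1−L), averaged over the number lost, with the cut-off recomputed for each remaining n. For d = 5% and p = 0.80: s = 0.7645, s + L = 0.8038 and s/(1−L) = 0.7958.

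**Step 4: Kaplan-Meier.** 40,000 simulated trials per setting. Reject if the one-sided 95% lower bound (Greenwood variance, log(−log) scale) exceeds 0.70. With no loss this gives type I error 0.045 and power 0.818, matching the exact test.

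**Results at n = 127 for d = 2%, 5%, 10%**

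| Handling of event-free losses | Power at 80% | Type I error at 70% | Bias at 80% (points) |
|---|---|---|---|
| Dropped | 78%, 75%, 69% | 3.4%, 3.0%, 2.2% | −0.2, −0.4, −0.9 |
| Counted as event-free | 83%, 85%, 87% | 5.1%, 5.9%, 7.7% | +0.2, +0.4, +0.8 |
| Counted as failures | 70%, 47%, 16% | 2.3%, 0.8%, 0.1% | −1.4, −3.6, −7.1 |
| Kaplan-Meier | 82%, 80%, 80% | 4.6%, 4.0%, 4.4% | about 0 |

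If all 140 are enrolled and evaluable, counting losses as event-free gives type I error of 4.2%, 5.0% and 6.7%.

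**Step 5: does the change alter a complete-data decision?** Without loss the log(−log) lower bound is 69.5% at 97/127 and 70.3% at 98/127. Both methods therefore reject from 98.

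**The case against.** The strongest objection is that losses may be very few. Treatment visits run every 28 days through 27 × 28 = 756 days, past the 2-year point. Stopping drug (section 9.1) is separate from leaving the study (section 9.2), remission status is still collected after therapy, and the synopsis intends follow-up until endpoints are met. This stands. At 1% loss, about one patient, power is 76% with losses as failures or 79% with losses dropped, and type I error is 4.8% with losses as event-free. But an intention to follow everyone does not say how to count those whom section 9.2 allows to leave.

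A second objection is that the binomial test is named only to justify the sample size. A reader might infer that the protocol commits itself to a raw count as the final analysis. It does not say so. The accurate statement is that no other Stratum 1 EFS analysis is given.

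A reader might also infer from the failure rule that power collapses. That rule is a worst case and fits section 10.4 poorly, because EFS time there ends at last contact without an event. Under dropping, most of the power loss comes from smaller n and discreteness, not bias.

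Nor is type I error inflated in every case. At n = 140 it stays below 5% at 2% loss and is about 5% at 5% loss. Counting losses as event-free also has little support in the text: the synopsis rule for Stratum 2 counts patients observed to reach 2 years.

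Finally, Kaplan-Meier is not the only remedy. A single stated counting rule would also close the gap, though dropping or failing losses gives up power and counting them as event-free biases the estimate upwards.

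**Conclusion.** The gap is real and should be closed before analysis. The Stratum 1 plan names a test that needs complete 2-year status, uses an efficacy set that does not guarantee it, and has neither a rule for event-free losses nor a Kaplan-Meier estimate of EFS.

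The sample size is not in dispute: with complete follow-up 127 patients give 82.0% power at an exact 4.5% type I error. It would be wrong to infer that the trial is underpowered as designed.

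The size of the effect depends on a loss rate that the documents do not give. It is small near zero loss. At an assumed 5% loss, about 5 patients, dropping costs 7 points of power (82% to 75%), while counting losses as event-free puts type I error at 5.9% with n = 127. Kaplan-Meier holds about 80% power and 4.0% type I error in the same setting. These figures rest on exponential event times and on loss that is independent of outcome.

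**What to change.** State in the SAP that the Stratum 1 primary analysis is the Kaplan-Meier estimate of 2-year EFS in the planned efficacy set, with a one-sided 95% complementary log-log lower bound compared with 70%. Keep the exact binomial count as a sensitivity analysis, with a rule fixed in advance for patients whose follow-up ends event-free before 2 years.

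The cost is wording only: no extra data, no change in sample size and, with complete follow-up, no change in the decision. The downsides are reliance on independent censoring and on a large-sample bound. The change also does not correct late detection of relapses first seen at the end-of-cycle-27 scan, nominally day 756 and so after 2 years. A count by detection date has the same problem.

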
STATISTICS/SAMPLE SIZE ESTIMATE
	
Statistics: All baseline subject characteristics will be summarized in a tabular format. Safety data will be described for all subjects receiving at least one dose of DFMO. Safety data will include values for hematology, serum chemistry, vital signs, and adverse events. The proportion of subjects experiencing adverse events, serious adverse events, and treatment delays will be summarized for each dosing cohort.
 
Sample Size: Stratum 1: A 70% 2-year EFS rate was selected as the Phase I baseline rate. The baseline 70% EFS rate at 2-years was based upon published data by Yu et al. It is hypothesized that DFMO will increase the 2-year EFS rate to 80% which represents an approximately 10% increase in the duration of the EFS rate at 2-years. Assuming a directional 5% one population binomial test, a sample size of $n = 127$ patients will be required to achieve an 80% power to detect this 2-year difference in EFS (70% vs 80%).
 
The comparison of the biomarker prevalence rates assumes that the Stratum 1 cohort will experience a relapse rate of 30% and a 70% non-relapse rate at up to two years of follow-up. It is also assumed that the corresponding prevalence of an elevated biomarker will be 60% for the relapse group and 30% in the non-relapse group, respectively. This hypothesized prevalence difference will be detectable with at least an 85% power with an overall sample size of $N=127$ patients (38 relapse and 89 non-relapse) using a Fisher’s Exact Test and a non-directional Type I Error level of 5%.
 
Stratum 2: Examination of EFS will require a sample size of $n = 33$ subjects in Stratum 2 to test whether treatment with DFMO can prolong the overall estimated EFS at two years to 30% from the 10% at two years estimate for the known historical data in this subject population. A one population binomial test with power 80% and a 5% two-tailed Type I error level will require $n = 33$ total patients
 
The one population binomial test will reject the null hypothesis that the two year EFS rate = 10% in favor of the EFS = 30% if 7 or more of the $n = 33$ patients are observed to have at least a two year EFS.

---	--

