The sequential biomarker data over the course of treatment for each patient will be classified as elevated or not based upon the following *a priori* study criteria and blinded to patient progression status. Elevation of the biomarker is defined as diacetylspermine levels > 500nmol/gm creatinine on 2 consecutive urine levels. The biomarker prevalence rates for the patients who progress (estimated to be n= 38) and those who do not progress (estimated n=89) over the two years of the trial treatment will be compared using a Fisher's exact test of the equality of the two EFS prevalence rates implemented with a 5% two-tailed Type I error level. A 95% exact confidence interval for the absolute difference in prevalence rates along with a 95% exact confidence interval for the odds ratio for the resulting prevalence rates will be obtained to complement the formal hypothesis testing. Since OS will also be a secondary outcome for comparing the utility of the biomarker prevalence, time-to-event analyses will also be implemented using the Kaplan-Meier approach initially using the *a priori* biomarker definition. These initial time-to-event analyses will then be supplemented with a Cox proportional hazard modeling effort using the quantitative biomarker assessment to allow for an exploratory analysis of other cut-point definitions that can be used to contrast with that of the original *a priori* definition. Potential confounding clinical measures that are identified for the recurrent and non-recurrent patients will be incorporated in a limited fashion using Cox proportional hazard models that also include the biomarker effect. This exploration of confounders will need to be limited due to the anticipated small sample sizes. Data from this stratum will guide the statistical design for a Phase II study in this patient population.

Stratum 2:

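### The urine-marker power in Stratum 1 assumes the no-effect relapse rate (30%); at the event rate the primary objective hypothesises (20%), the stated 85% becomes about 76%

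*Combined protocol and SAP*

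**What the plan says.** All of this is in Section 10, Sample Size and Analysis, Stratum 1, and is largely repeated in the synopsis under Statistics/Sample Size Estimate.

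- **Primary objective, null rate:** "A 70% 2-year EFS rate was selected as the Phase I baseline rate".
- **Primary objective, alternative:** "It is hypothesized that DFMO will increase the 2-year EFS rate to 80" percent. The test is a one-sided 5% one-sample binomial test with n = 127 and 80% power.
- **Marker objective, relapse rate:** the comparison "assumes that the Stratum 1 cohort will experience a relapse rate of 30% and thus a 70% non-relapse rate at up to two years".
- **Marker objective, effect:** "prevalence of an elevated biomarker will be 60% for the relapse group and 30% in the non-relapse group", compared by Fisher's exact test, two-sided 5%.
- **Marker objective, power:** "This hypothesized prevalence difference will be detectable with 85% power with an overall sample size of N=127 patients (38 relapse and 89 non-relapse"). The synopsis is slightly stronger: "detectable with at least an 85% power".
- **Analysis text:** the same split is carried forward: "The biomarker prevalence rates for the patients who progress (estimated to be n= 38"), with 89 who do not progress.

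The Event Free Survival section counts relapse, progression, secondary cancer and death as events. The documents give no marker power at a 20% event rate and no reason for planning the marker comparison on 30%.

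**The concern.** The two objectives use the same 127 treated patients but assume different event rates. The primary objective expects DFMO to lower the 2-year event rate from 30% to 20%. The marker objective needs the 30% that would occur if DFMO did nothing. An effective drug removes the progressors on whom the marker comparison depends.

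Correlation of urinary polyamines with progression is a named secondary objective, with its own pre-set cut-off, formal test and power claim. The plan also says that Stratum 1 data will inform the design of a later study. If the trial is positive and the marker test is not significant, a reader relying on 85% power would give that null result more weight against the marker than it deserves.

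**Working it through.** **Inputs (Section 10, Stratum 1).** N = 127; elevated marker in 60% of relapsed and 30% of non-relapsed patients; Fisher's exact test, two-sided 5%; null EFS 70%; hypothesised EFS 80%.

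**Method.** For group sizes n1 (relapse) and n2 (non-relapse), power is the sum of Bin(x; n1, 0.60) × Bin(y; n2, 0.30) over all pairs (x, y) whose two-sided Fisher p-value is at most 0.05.

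**Step 1: reproduce the stated figure.** 127 × 0.30 = 38.1, giving 38 versus 89. Exact power is 86.9%, which agrees with the synopsis claim of at least 85%. A continuity-corrected normal approximation gives 84.9%, and a one-sided Fisher test at 2.5% gives 84.7%. The 85% is sound on its inputs.

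**Step 2: use the hypothesised EFS rate.** 127 × 0.20 = 25.4, giving 25 versus 102.

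| Relapse / non-relapse | Scenario | Exact power |
|---|---|---|
| 38 / 89 | 70% EFS, as planned | 86.9% |
| 35 / 92 | fewest relapses that keep 85% | 85.9% |
| 34 / 93 | one fewer | 84.4% |
| 32 / 95 | 75% EFS | 82.4% |
| 29 / 98 | most events a positive primary result allows | 80.4% |
| 26 / 101 | 80% EFS, 25.4 rounded up | 78.4% |
| 25 / 102 | 80% EFS | 76.0% |

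Other methods at 25 versus 102 give 72.2% (one-sided Fisher at 2.5%), 72.7% (continuity-corrected) and 79.8% (uncorrected normal approximation). None reaches 80%.

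The chance of missing the difference rises from 100 − 86.9 = 13.1% to 100 − 76.0 = 24.0%. Treating the relapse count as random, Binomial(127, rate), gives an average power of 86.1% at a rate of 0.30 and 75.6% at 0.20.

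**Step 3: where 29 comes from.** The plan gives no rejection count for Stratum 1, so I derived it. With n = 127 and null 70%, rejecting at 98 or more event-free patients has a one-sided error of 4.5%; rejecting at 97 would have 6.8%. Power at 80% EFS is 82.0%. A positive primary result therefore means at most 127 − 98 = 29 events. Keeping 85% marker power needs about 35 relapses. With 127 fully followed patients, both cannot happen.

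**Step 4: relapses are a subset of EFS events.** The 25 is an upper figure for relapses at 80% EFS. As an illustration, if 22 of the 25 events were relapses (22 versus 105), power would be 71.4%.

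**The case against.** **The 85% is not a miscalculation.** It reproduces from openly stated inputs, and a reader can see that it depends on a 30% relapse rate. This stands: the fault is an inconsistent planning assumption.

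**A secondary comparison need not be powered under the primary alternative.** The marker question exists whether or not DFMO works, and 70% is the rate with a published basis. That is fair, but the plan does not argue it. For this test, 30% is also the favourable choice, and it is the only one shown.

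**The 76% is one point in a range.** Rounding up to 26 events gives 78.4%. The synopsis allows up to 140 patients; if all were evaluable, 28 versus 112 gives 80.6%. A positive trial with exactly 29 events has 80.4%. These are correct, but none restores 85%, and deaths and second cancers push the figure down.

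**The prevalences matter at least as much.** They have no stated source. At 38 versus 89, a 55% versus 30% difference has 72.6% power; at 25 versus 102, 65% versus 30% has 88.1%. This stands as a caveat. It does not remove the conflict, since the plan's own 60% and 30% are held fixed in the comparison above.

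**Part of the remedy is already planned.** Exact 95% intervals for the prevalence difference and the odds ratio are specified, and the plan admits small samples when it discusses confounders. So the interval advice needs only a sentence, while the power statement still needs correcting.

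**Conclusion.** The concern holds. The marker power in Stratum 1 is computed at the no-effect rate of the primary test. At the rate the trial hypothesises, exact power is about 76% rather than 85%, a fall of 10.9 percentage points from the 86.9% that the same test gives at 38 versus 89. No positive primary result in 127 fully followed patients brings marker power above about 80%.

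This rests on the plan's 60% and 30% prevalences, on 127 evaluable patients, and on every EFS event being a relapse or progression. The last assumption is generous to the plan. The primary test, its error rate and the sample size are unaffected. It is a moderate point on a secondary objective, and it should be corrected because the figure is stated as a property of the design.

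**What to change.** 1. In Section 10 (Stratum 1) and the synopsis, replace the single power figure with two: about 87% if 2-year EFS is 70% (38 versus 89) and about 76% if it is 80% as hypothesised (25 versus 102). Say that both hold the 60% and 30% prevalences fixed and count every EFS event as a relapse.
2. In the analysis paragraph on the marker, replace the single estimate of 38 and 89 with both scenarios.
3. Add one sentence saying that a non-significant marker result will be interpreted through the planned exact 95% intervals for the prevalence difference and odds ratio, and not through the planning power.

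The cost is wording only. The stated secondary power becomes less favourable. Patient numbers, procedures, the test and the error level stay as they are.
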